Cover Page for ClinicalTrials.gov

Official Study Title:

Evaluation of a Cultural Dexterity Training Program for Surgeons: The PACTS Trial

NCT Number:

NCT03576495

Document:

Study Protocol

Document Date:

September 18, 2020

**PARTNERS HUMAN RESEARCH COMMITTEE
PROTOCOL SUMMARY**

Answer all questions accurately and completely in order to provide the PHRC with the relevant information to assess the risk-benefit ratio for the study. Do not leave sections blank.

PRINCIPAL/OVERALL INVESTIGATOR

[name], MPH

PROTOCOL TITLE

The Provider Awareness and Cultural Dexterity Toolkit for Surgeons (PACTS) Trial

FUNDING

1R01MD011685-01A1

VERSION DATE

September 18, 2020

SPECIFIC AIMS

Concisely state the objectives of the study and the hypothesis being tested.

Racial disparities in surgical care have been well-documented. In response to the IOM's 2003 recommendations on taking a multi-pronged approach to alleviating disparities that includes cultural competency training, we have proposed cultural dexterity, rather than cultural competency, as a modality for imparting such training to surgical residents. The purpose of this protocol is to test the impact of this new curriculum, called Provider Awareness Cultural Dexterity Toolkit for Surgeons (PACTS), on surgical residents' cross-cultural knowledge, attitudes, and skills surrounding the care of diverse patients, as well as patient-reported and clinical outcomes for patients treated by surgical residents undergoing this training.

1. Aim 1: Evaluate the impact of PACTS on surgical residents' knowledge and attitudes about caring for culturally diverse patients using a pre- and post-assessment.
Hypothesis 1: Residents receiving PACTS will show greater improvement in knowledge and attitudes compared to those who did not.
2. Aim 2: Determine the impact of PACTS on surgical residents' cross-cultural skills as demonstrated in a simulated clinical setting, using an Objective Structured Clinical Examination (OSCE) and by self-report. Each OSCE station will assess one of the four core topics covered by the PACTS training.

Hypothesis 2: Residents receiving PACTS will demonstrate greater improvements in cross-cultural skills.

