In anticipation of this protocol, we have pilot-tested the curriculum at three affiliated institutions with general surgery residents at varying levels of training. Focus group data was collected to garner feedback on the effectiveness and feasibility of the curriculum. **The purpose of the current protocol is to implement the curriculum across eight institutions and measure resident-level competency outcomes, as well as patient-reported and clinical outcomes, following this training.**

RESEARCH DESIGN AND METHODS

Briefly describe study design and anticipated enrollment, i.e., number of subjects to be enrolled by researchers study-wide and by Partners researchers. Provide a brief summary of the eligibility criteria (for example, age range, gender, medical condition). Include any local site restrictions, for example, "Enrollment at Partners will be limited to adults although the sponsor's protocol is open to both children and adults."

We will conduct a cross-over, cluster-randomized trial at 8 academic medical centers (AMCs) to capture the effect of PACTS on: 1) resident knowledge and attitudes regarding cross-cultural health care [Specific Aim (SA)1], 2) interpersonal and communication skills in simulated patient-clinician encounters [SA2], and 3) patient-reported satisfaction with resident physicians involved in their care, and clinical outcomes [SA3]. Sites will be assigned to an early intervention/retention assessment group or a control group with delayed intervention for examination of the effectiveness of the intervention as well as learner retention. After cluster-randomization, we will assess the residents' knowledge, attitudes, and skills prior to and after the PACTS curriculum at half the sites (Early Intervention/Retention Group). We plan to conduct follow-up testing after one year to evaluate learner retention.

At the other sites (Delayed Intervention Group), we will conduct baseline testing prior to the standard residency curriculum, and administer the PACTS curriculum the following year. This study design will enable us to examine both between- and within-group differences based on curriculum exposure in intervention year 1 as well as within-group differences for the Delayed Intervention Group at the end of year 2. Further, we will also be able to test post-exposure effect retention in the Early Intervention Group at the end of year 2.

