To evaluate the impact of PACTS on surgical residents' knowledge and attitudes about caring for diverse patients, we will use a pre- and post-test in the form of validated instruments that assess knowledge, attitudes, and self-reported skills on a Likert-type scale. This pre- and post-test will be piloted among a group of surgical residents (N=40) to assess the survey length and clarity of questions. Residents will be recruited using a convenience sampling method from those who participated in the surgery focus groups at ASC 2019. Exclusion criteria from this pilot will be residents at one of the trial AMCs.

Resident skills will also be objectively assessed through an Objective Structured Clinical Examination (OSCE) that will be created by the study

staff and administered immediately before the intervention and within 1-6 months after the intervention has been completed. The OSCE uses 5-point Likert scale questions to evaluate resident performance across multiple domains. A Standardized Patient evaluator and a third-party trained impartial observer will evaluate the residents on these domains, and the resulting numerical scores will be averaged. It will serve both a summative and educational purpose in this context. Due to the COVID-19 pandemic, in order to adhere to social distancing protocols, the OSCE may also be delivered virtually using a secured web-based video-conference software.

We have also developed a novel survey instrument to assess resident knowledge, attitudes, and self-reported skills. This instrument is adapted from pre-existing, validated instruments such as the Cultural Competence Health Practitioner Assessment (CCHPA), developed by the National Center for Cultural Competence, and modified to be relevant to surgical training and practice. Residents will be required to take a knowledge survey before and after receiving the PACTS curriculum or standard training. Attitudes regarding the importance of facing cross-cultural health care situations will be assessed across multiple domains using a novel survey instrument that is based on a survey that was used in a similar curriculum aimed at medical students, as well as the Values and Belief Systems domain.

Patients

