[https://partnershealthcare-public.sharepoint.com/ClinicalResearch/Guidelines For Advertisements.1.11.pdf](https://partnershealthcare-public.sharepoint.com/ClinicalResearch/Guidelines%20For%20Advertisements.1.11.pdf)

Remuneration for Research Subjects

[https://partnershealthcare-public.sharepoint.com/ClinicalResearch/Remuneration for Research Subjects.pdf](https://partnershealthcare-public.sharepoint.com/ClinicalResearch/Remuneration%20for%20Research%20Subjects.pdf)

CONSENT PROCEDURES

Explain in detail how, when, where, and by whom consent is obtained, and the timing of consent (i.e., how long subjects will be given to consider participation). For most studies involving more than minimal risk and all studies involving investigational drugs/devices, a licensed physician investigator must obtain informed consent. When subjects are to be enrolled from among the investigators' own patients, describe how the potential for coercion will be avoided.

Focus Groups

Participants will be provided a fact sheet that contains information regarding the focus group that they will be participating in. Consent will be indicated either through completion of an online registration form or through participation in the focus group.

Survey Pilots

Participants will be provided with a fact sheet that contains information regarding the survey pilot. Consent will be indicated through voluntary completion of the survey.

Residents

Each program director will initiate recruitment for their site and provide email contacts, but a research assistant will enroll and consent residents. Following the didactic curriculum and prior to the first testing sessions, residents will review an informational sheet that they may keep for reference. Completing the resident surveys will indicate consent to participate in the study. Prospective subjects will be reminded that their decision to enroll in the study will remain confidential, as will their performance evaluations if they choose to participate. De-identified informed

consent documents will be maintained by the research assistant in a locked folder on-site or on a protected and secure database.

Patients

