Cover Page for ClinicalTrials.gov

Official Study Title:

Evaluation of a Cultural Dexterity Training Program for Surgeons: The PACTS Trial

NCT Number:

NCT03576495

Document:

Statistical Analysis Plan

Document Date:

June 6, 2017

PACTS ANALYSIS PLAN: The multi-year cluster-randomized study design will enable us to examine differences between and within the Early Intervention and Control/Delayed PACTS training groups across three unique time points (Year 2 pre-intervention, Year 2 post-intervention and Year 3 post-intervention). Details of statistical measures/methods and power calculations appear below.

Within-group differences (repeated measures).

Repeated measure differences on dichotomous outcomes will be examined using Chi-square and Fisher's exact tests, as well as unadjusted logistic regression models controlling for resident-specific demographic factors (e.g. age, IAT, post-graduate year, and sex).

Differences in ordinal outcomes (e.g. three- or five-point Likert scale reporting or ordered category scores) between pre- and post-intervention testing will be examined using Chi-square tests, unadjusted ordered logistic regression, and ordered logistic regression adjusted for resident- and program-specific factors. Table 7 depicts our sample size/power calculations, according to which we will be able to detect an 11% absolute difference in the proportion achieving "adequate" vs. "sub-optimal" dichotomized assessments before and after PACTS training. This accounts for an up to 20% sample loss from the expected 200 enrolled residents per group.

Between-group differences (independent measures). Pre- vs. post- differences in both self-reported and observer-assessed ordinal outcomes between the Early and Delayed Intervention groups will be assessed at the end of the first training period using Chi-square tests and unadjusted ordered logistic regression, as well as ordered logistic regression models controlling for resident- and program-specific factors. Previous work demonstrated that exposure to training similar to PACTS was associated with a 20-25% increase in the proportion of trainees achieving "adequate" scores on an OSCE-based assessment. Based on the number of residents in each arm (n=200), we anticipate that we will be able to detect a much smaller between-group difference even with up to 20% sample attrition over time (Table 7).

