Between group resident knowledge/ Skills/attitudes	Post-test proportion in Early Group vs. Delayed Group achieving "adequate" vs. "sub-optimal" dichotomized assessments	Early Group: 159 Delayed Group: 159 (Independent Measures)	Change from 50% to 65.5% Assuming remains at 50% with no change from baseline assessment. Thus, we would be able to detect a 15% relative proportional difference between groups associated with exposure to PACTS training.
Patient-reported within and between-group differences			
Patient-reported outcomes	Pre- vs. Post-test proportion of patients reporting pain-satisfaction scores in the uppermost standardized quintile	Pre-intervention: 361 Post-intervention: 361 (Independent Measures)	Proportion of Patients with scores Pre-intervention: 63.0% Post-intervention: 73.0% Thus, we expect to be able to detect an absolute proportional difference of 10%.
Sample size/power calculation for NSQIP outcomes			
Readmissions	Pre- vs. Post-test proportion of patients readmitted	Pre-Intervention: 377 Post-intervention: 377	Proportion of Patients readmitted Pre-intervention: 23% Post-intervention: 15%

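### The year-1 Early-vs-Delayed resident analysis should state its response and name the resident's own pre-test as a covariate

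*SAP*

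**What the plan says.** The SAP paragraph on between-group differences (independent measures) concerns the close of the year-1 training period, and its subject is "Pre- vs. post- differences in both self-reported and observer-assessed ordinal outcomes between the Early and Delayed Intervention groups". The methods are Chi-square tests, unadjusted ordered logistic regression, and "ordered logistic regression models controlling for resident- and program-specific factors". The between-group paragraph does not list those factors. The only examples are in the within-group paragraph: "resident-specific demographic factors (e.g. age, IAT, post-graduate year, and sex".

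The between-group resident row of Table 7 compares post-test proportions reaching the adequate level, as independent measures, with 159 residents per group and a change from 50% to 65.5%. Its note on the comparison group reads "Assuming remains at 50% with no change from baseline assessment".

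In the Protocol, Hypothesis 1 (Specific Aims) is that "Residents receiving PACTS will show greater improvement in knowledge and attitudes compared to those who did not". Under Research Design and Methods, Early sites are tested before and after PACTS, and for Delayed sites "we will conduct baseline testing prior to the standard residency curriculum". The Residents part of the study procedures adds: "Residents will be required to take a knowledge survey before and after receiving the PACTS curriculum or standard training". The Residents paragraph of Consent Procedures, however, places the information sheet "Following the didactic curriculum and prior to the first testing sessions".

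**The concern.** Three analyses fit the SAP's phrase: a change category, a group-by-time contrast, and a post-test comparison between arms. They differ in power, and if none is fixed in advance the choice can be made after the results are seen. The hypothesis is about improvement, and with only eight randomised sites a chance difference between arms at baseline is plausible. The resident's own pre-test is the obvious covariate and is already planned in both arms, yet the SAP does not commit to using it. What is at stake is mainly precision, and protection against a choice of response made after the fact.

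**Working it through.** **1. The plan's own figure.** Pooled two-proportion formula, two-sided 0.05, 80% power, p1 = 0.50, p2 = 0.655, mean 0.5775:

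n = [1.960 × √(2 × 0.5775 × 0.4225) + 0.842 × √(0.50 × 0.50 + 0.655 × 0.345)]² / 0.155² = 158.2, so 159 per group.

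Table 7 reproduces. It is a post-test calculation and takes no precision from the baseline. Because it assumes the comparison group stays at 50%, its expected difference equals the expected difference in change, so it does not contradict the text.

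**2. Inputs for comparing the analyses.** From the documents: 8 sites, half per arm, and 200 residents per arm less 20%, which is 160 per arm or 40 per site. The effect of 50% vs 65.5% is a latent shift of 0.399 SD (inverse normal of 0.655). Assumed, because the documents give none: ICC 0.01 or 0.05; resident pre/post correlation r = 0.3, 0.5 or 0.7; correlation s of a site's level between the two times = 0, 0.3 or 0.7. That makes 18 scenarios. Table 7's within-group row (160 residents, 50% to 61%) is consistent with r near 0.5 under a McNemar formula, which gives 164. This is an inference about the dichotomised score, so the range is kept.

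**3. Variance of a site mean** (total variance 1, w = (1 − ICC)/40):
- post-test alone: ICC + w
- change: 2·ICC·(1 − s) + 2w(1 − r)
- post-test adjusted for pre-test, slope r: ICC·(1 + r² − 2rs) + w(1 − r²)

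At ICC 0.01, r = 0.5, s = 0.3, w = 0.02475:
- post-test: 0.0348
- change: 0.0140 + 0.0248 = 0.0388
- adjusted: 0.0095 + 0.0186 = 0.0281

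At ICC 0.05, r = 0.5, s = 0, w = 0.02375:
- post-test: 0.0738
- change: 0.1238
- adjusted: 0.0625 + 0.0178 = 0.0803

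In the second case the adjusted variance exceeds the post-test variance, because the site's pre-test level then adds only noise. With standard error √(variance/2) and a t test on 6 df, these formulas over all 18 scenarios give adjusted minus change of +4 to +21 points of power, and adjusted minus post-test of −5 to +27.

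**4. Simulation on the planned type of model.** Ordered logistic regression on five categories (cut-points assumed at ±0.5 and ±1.5 SD), site-level t test on 6 df, 4,000 trials per scenario. Power in %, at r = 0.5:

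| ICC | s | post-test, no covariate | change category | post-test + pre-test |
|---|---|---|---|---|
| 0.01 | 0 | 67.6 | 56.8 | 72.5 |
| 0.01 | 0.3 | 67.8 | 60.1 | 75.7 |
| 0.01 | 0.7 | 67.6 | 69.0 | 80.6 |
| 0.05 | 0 | 39.4 | 26.1 | 38.5 |
| 0.05 | 0.3 | 40.3 | 31.5 | 44.3 |
| 0.05 | 0.7 | 39.8 | 47.4 | 55.3 |

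Over the 18 scenarios adjustment beat the change category every time, by 6 to 21 points; a separate check with t tests on category scores gave about 5 to 23. It beat the post-test alone in 15 of 18, with a range of −4 to +25. The three losses (0.8, 0.9 and 4.3 points) were all at ICC 0.05 with s = 0. Type I error was 4.2 to 5.9%. Only differences between columns bear on this point; the absolute levels reflect clustering.

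**5. Why the timing must be settled.** If a fraction f of Early pre-tests followed exposure, the share of the effect lost is about f × slope. The slope is 1 for a change score, 0.27 to 0.63 for the adjusted model (r = 0.3 to 0.7), and 0 for the post-test alone. At f = 20% the losses are 20%, about 5 to 13%, and none.

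**6. Missing pre-tests.** With 20% missing at random and r = 0.5, power at s = 0 / 0.3 / 0.7 was:
- ICC 0.01: complete pairs 67 / 68 / 73%, all post-tests kept 73 / 74 / 78%
- ICC 0.05: complete pairs 38 / 42 / 54%, all post-tests kept 41 / 45 / 56%

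**The case against.** The strongest reply is that the response is not really missing. The paragraph is headed as independent measures and refers to the end of the first training period, and Table 7 names a post-test comparison. This largely stands: a reader might infer that the SAP has no response, or that text and table conflict, and neither is supported. What remains is that the text's phrase also fits other analyses, and that Table 7 dichotomises while the text is ordinal.

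Second, a reader might infer that baseline adjustment is excluded. It is not: the examples are introduced by e.g., sit in another paragraph, and could include a pre-test score. The gap is the lack of a commitment.

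Third, the comparators are not exactly the plan's. The change category (grouped from −2 or lower to +2 or higher) was constructed for this check, and the group-by-time contrast was not simulated. The post-test model has no covariates, whereas the SAP also plans adjusted models. If those covariates explain 10% or 20% of resident variance in both tests (assumed), the gain at ICC 0.01, r = 0.5, s = 0.3 falls from 8.6 points to 6.7 or 4.9 on a linear approximation. This stands: the quoted gains over the post-test are at the high end for the adjusted analysis.

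Fourth, a reader might infer from the consent wording that Early pre-tests were taken after the curriculum. No document says so, and the design and procedures sections say the opposite. It is an inconsistency to resolve, and the losses in step 5 are hypothetical.

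**Conclusion.** The point holds as a gap in specification. The SAP should say which response it analyses in year 1 and should commit to the pre-test as covariate. Under the assumed ICC of 0.01 to 0.05, resident correlation of 0.3 to 0.7 and site correlation of 0 to 0.7, the simulated gain is about 5 to 23 points of power over a change score. Over a post-test model with no covariates it is about −4 to +25 points, and smaller where the planned covariates already predict the scores. The advantage over a change score held in every scenario tried; the advantage over the post-test did not. It would be wrong to conclude that adjustment always helps or that the sample size is miscalculated: 159 is correct for its own inputs. Clustering, degrees of freedom under program matching, and required versus voluntary testing are separate matters. Priority is modest.

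**What to change.** - First reconcile the Residents paragraph of Consent Procedures with Research Design and Methods and the Residents procedures on when residents receive the information sheet and take the first test. Use as covariate only pre-tests taken before exposure.
- Keep the planned ordered logistic regression. State that the response is the post-test category, in line with Table 7. Make the primary year-1 between-arm model the post-test on arm plus the resident's own pre-test of the same measure, alongside the planned covariates.
- Keep residents who have a post-test but no pre-test by a rule stated in advance, for example the overall-mean baseline with a missing indicator. Report pre-test completion by arm and add a complete-pairs sensitivity analysis.
- Note that Table 7 is an unadjusted post-test calculation.

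The cost is SAP wording and one reconciliation in the Protocol, with no new data collection. The downside is that, at an ICC of about 0.05 with site levels unrelated over time, adjustment gives no gain and may cost up to about 4 to 5 points of power against a post-test alone. The missing-indicator rule assumes that pre-test completion does not depend on arm and ability together, hence the completion table and the sensitivity analysis.

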We are partnering with eight general surgery residency programs and their affiliated hospitals to conduct the PACTS Trial. Programs have been matched to achieve balanced cohorts in terms of program size and diversity of patient population. Based on case mix, we anticipate approximately 40% of the patient population in this study will be of minority descent. The eight programs that will be participating in this study are: 1) Johns Hopkins University, 2) Brigham and Women's Hospital, 3) Brown University, 4) Eastern Virginia Medical School, 5) Massachusetts General Hospital, 6) Beth Israel Deaconess Medical Center, 7) Howard University, and 8) Washington University in St. Louis.

Briefly describe study procedures. Include any local site restrictions, for example, "Subjects enrolled at Partners will not participate in the pharmacokinetic portion of the study." Describe study endpoints.

Surgery Focus Group

In anticipation of the implementation of the cross-over, cluster-randomized trial at the 8 academic medical centers, we hope to gather feedback from surgical residents, medical students, and surgical faculty in training programs outside of these sites to assist in the development of the cultural dexterity curriculum. We believe that surgical conferences would be the best opportunity to gain insight regarding the current curriculum content as well as curriculum implementation. Contributions from surgical residents, medical students, and surgical faculty will be important to supplement the previous input from surgical faculty and program directors.

We plan to recruit participants from the surgical specialty excluding those from our 8 academic medical centers. We will disseminate one of four modules of the curriculum in advance for review. Participants will then be scheduled for a 1 hour-long focus group based on their availability, with a total of four focus groups. Focus groups will be facilitated by two study staff in a semi-structured focus group model. We believe this input will be integral in ensuring that our cultural dexterity curriculum can eventually be implemented in all surgical training programs across the country.

Patients Focus Group

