All general surgery residents will receive the educational curriculum; each site's Program Director (PD) has agreed to schedule PACTS training during compulsory didactic sessions, when residents are free from clinical duties. However, participation in study assessments (OSCEs and knowledge-testing) is voluntary and will not impact residents' performance in their program. Final analyses will include enrolled residents regardless of their attendance in live modules, reflecting an "intention-to-treat" analysis approach. This will more accurately demonstrate the "real world" benefit of PACTS, as not all residents may be able or willing to attend all live sessions. Based on the size of the residency programs, which ranges between 46 and 72 residents, and the away rotation schedules, we expect to enroll 200 residents per arm for analysis (an average of 50 residents per site).

Patient Recruitment

At the onset of clinical rotations, the Program Manager will contact surgical residency Program Coordinators to attain general surgery resident rotation schedules. The Program Manager will identify the dates and times of resident study participants' rotations. On these dates and times, Research Assistants working under the supervision of the Program Manager will verify that the resident is on rotation and use the EHR at the surgical service site to

randomly select at least two eligible patients from the EHR. First, the RA will approach the patients' nurse and ask whether the nurse might have a concern regarding the selected patients' cognitive status. If the nurse has no concerns, the nurse will be asked to introduce study staff to the patient. Staff will provide an information sheet, describe the study, and ask them to identify a resident participating in the PACTS trial who they recall interacting with. The RA will explain the study and provide the patient with a copy of the Patient Information Sheet and survey, which will be administered via tablet or laptop computer to access the survey in the Partners-hosted REDCap database. Completion of the English or Spanish language survey will indicate consent to participate in the study and the patient will be enrolled.

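### Eight sites are randomised, but the Early vs Delayed resident comparison and Table 7's 159 per group treat residents as independent

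*SAP*

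**What the plan says.** The Protocol's Research Design and Methods section states: "We will conduct a cross-over, cluster-randomized trial at 8 academic medical centers (AMCs"). Half the sites receive PACTS first, which gives four against four. Resident Recruitment expects 200 residents per arm, on average 50 per site. The SAP's opening paragraph also calls the design cluster-randomised.

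Under Between-group differences, the SAP takes as its outcome "Pre- vs. post- differences in both self-reported and observer-assessed ordinal outcomes between the Early and Delayed Intervention groups". These "will be assessed at the end of the first training period using Chi-square tests and unadjusted ordered logistic regression", followed by ordered logistic models adjusted for resident and program characteristics. On power, it says "we anticipate that we will be able to detect a much smaller between-group difference even with up to 20% sample attrition" than the 20-25% increase it cites from earlier work.

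Table 7's between-group row describes a different contrast: "Post-test proportion in Early Group vs. Delayed Group achieving" an adequate score, 50% vs 65.5%, at 80% power and alpha 0.05. Its group sizes read "Early Group: 159 Delayed Group: 159 (Independent Measures").

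The Protocol also reports that "Programs have been matched to achieve balanced cohorts in terms of program size and diversity of patient population", but matching appears in neither the analysis nor the sample size. No ICC or design effect is given, and no method for correlated residents.

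**The concern.** Residents of one program share faculty, case mix and teaching, and PACTS is delivered in each program's scheduled didactic sessions. Some correlation within a program is therefore plausible. Chi-square and ordinary ordered logistic regression compute the standard error as if about 320 residents had been randomised one by one. In fact eight units were randomised, and the arm contrast carries the between-program variance.

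This is the trial's only randomised comparison and the test of Hypotheses 1 and 2. If the standard error is too small, ordinary differences among eight programs can be reported as an effect of PACTS, and the stated 80% power overstates what the design can deliver.

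**Working it through.** **Inputs.** From the documents: 8 sites, 4 per arm; 200 residents per arm less 20% loss = 160, so 40 per site; proportions 50% and 65.5%; alpha 0.05; power 80%. Assumed: two-sided testing (the side is not stated, but two-sided reproduces Table 7) and an ICC of 0.001 to 0.05.

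**1. Table 7's own figure.** Pooled two-proportion formula with mean proportion 0.5775:

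n = [1.96·√(2·0.5775·0.4225) + 0.8416·√(0.5·0.5 + 0.655·0.345)]² / 0.155² = 158.2, rounded up to 159.

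The match needs no design effect.

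**2. Type I error of the planned test on post-test proportions.** DEFF = 1 + (40 − 1)·ICC, and actual error = 2·[1 − Φ(1.96/√DEFF)]. The simulation drew beta-binomial sites, 4 vs 4 with 40 residents each, 100,000 replicates.

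**3. A test that respects the randomised unit.** For a t-test on eight site proportions (6 df, critical value 2.447), SE = √[(0.25 + 0.225975)·DEFF/160] and the noncentrality is 0.155/SE: 2.41, 2.13 and 1.65 at ICC 0.01, 0.02 and 0.05. The last column solves the same expression for 80% power.

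| ICC | DEFF | Chi-square error, formula | Chi-square error, simulated | Site t-test power, 50% vs 65.5% | Difference detectable with 80% power |
|---|---|---|---|---|---|
| 0 | 1 | 5.0% | – | 66% | 18 points |
| 0.001 | 1.039 | 5.5% | 5.6% | 64% | 19 points |
| 0.005 | 1.195 | 7.3% | 7.2% | 59% | 20 points |
| 0.01 | 1.39 | 9.6% | 9.7% | 53% | 21 points |
| 0.02 | 1.78 | 14.2% | 14.1% | 43% | 24 points |
| 0.05 | 2.95 | 25.4% | 25.6% | 29% | 29 points |

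In simulation the site t-test held 5.0-5.2%. If matched pairs are analysed (3 df), power is about 39%, 32% and 22% at ICC 0.01, 0.02 and 0.05, before any gain from matching.

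**4. If change is compared.** Let f be the share of site variance that changes between tests and r = 0.5 the assumed within-resident correlation. Then ICC of change = f·ICC / [f·ICC + (1 − ICC)(1 − r)], put through the same error formula.

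| f | ICC 0.01 | ICC 0.02 | ICC 0.05 |
|---|---|---|---|
| 0 (fully stable site effects) | 5.0% | 5.0% | 5.0% |
| 0.25 | 7.3% | 9.7% | 16.6% |
| 0.5 | 9.6% | 14.2% | 25.4% |

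**5. Does adjusting for program factors cure it?** An ordinary binary logistic model stood in for the adjusted ordered model (post-test contrast, 3,000 replicates). At ICC 0.01, 0.02 and 0.05 the error was 9.4%, 15.1% and 26.3% with an uninformative program covariate. With a covariate explaining half the site variance it was 7.5%, 9.2% and 16.2%. A full set of program indicators is not available in a post-test model, because it would be collinear with arm.

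**6. Power after baseline adjustment.** Adjusting each resident for their own baseline (slope 0.5, linear approximation) replaces DEFF by 0.75·(1 − ICC) + 40·k·ICC. Here k = 0.5 if a quarter of the site variance shifts, and 0.25 if none does. On 6 df, power at ICC 0.01, 0.02 and 0.05 is about 69%, 61% and 45% in the first case, and 73%, 69% and 58% in the second.

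**The case against.** The best counter-argument concerns the contrast. Hypotheses 1 and 2 speak of greater improvement, and the SAP's test sentence concerns pre-to-post differences; only the Table 7 row refers to post-test proportions. If change is what is tested, stable program effects cancel and the error may be as low as 5%. This stands as a limit on the size: the 10-25% belongs to the post-test reading. It does not rescue the plan, because full stability is itself an assumption, and the documents do not settle which contrast applies.

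The ICC is wholly assumed, and below 0.005 the inflation is small. That also stands. The omission is certain; its size is not.

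Part of the power loss comes from having 6 df rather than from correlation: 80% falls to 66% at ICC 0, and only the further drop to 53% at ICC 0.01 is due to clustering. Baseline adjustment recovers a good part of it. Both points are right and should accompany the lower figures. Even so, every adjusted figure above is below 80%.

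Matching and program-level covariates may reduce between-site variance, but neither corrects the standard error of the arm contrast. Finally, a mixed model or GEE with a small-sample correction could serve as primary instead of a site-level t-test. That is a choice between valid methods and no defence of the written one.

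**Conclusion.** The concern holds and must be fixed. The SAP's randomised comparison and its Table 7 row ignore the unit of randomisation; the exact reproduction of 159 with a design effect of 1 confirms this.

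At an assumed ICC of 0.01-0.05 with 40 residents per site, the planned post-test comparison has about 10-25% type I error. For change the range is 5-17% when no more than a quarter of the site variance shifts, and it is higher if site effects are less stable.

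The 80% power for 50% vs 65.5% does not hold for a site-level test at any ICC considered, including zero. At ICC 0.01 and 0.02 the detectable difference of 21 and 24 points lies within the 20-25% effect the SAP cites, if that figure is absolute; at 0.05 it lies above. The claim of detecting a much smaller difference therefore fails from ICC 0.01 upward for this test without baseline adjustment.

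The patient pre-post tests also ignore nesting within site and resident, but no error rate is claimed for them here.

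**What to change.** 1. State whether the primary Early vs Delayed contrast is post-test level or change, and make the SAP text and Table 7 agree.
2. Make the primary test a t-test on site means adjusted for each resident's own baseline score, on 6 df, or fewer if randomisation was within matched pairs. The SAP should say which. Support it with a mixed ordinal model that has a random site intercept and small-sample degrees of freedom; the reverse order is also defensible if fixed in advance.
3. Keep chi-square and ordinary ordered logistic results as descriptive, and report the observed ICC.
4. Restate Table 7's between-group row with an assumed ICC, its design effect and the small degrees of freedom. The row should also call the 15.5-point difference absolute; it is now labelled relative.
5. Account for site and resident nesting in the patient pre-post models.

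The cost is SAP text and modest extra analysis, with no new sites, participants or visits. The real price is wider intervals and a lower stated power: about 53%, 43% or 29% at ICC 0.01, 0.02 or 0.05 without baseline adjustment, and roughly 45-73% with it under the assumptions above.
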